#### Randomization:

Randomization will be computerized.

#### Blinding:

Open, no blinding will be used.

#### Sample size:

The significance level (Alpha) will be 5%, power (1-beta) 80%. The composite major adverse event rate (all-cause mortality, AMI, cerebral vascular event, BARC type 3 or type 5) in the CR group was set at 4.19% based on the RIVAL study and with a non-inferiority cutoff of 1.89%. In the presence of a true difference in favor of the experimental group of 1.89%, the total population required is 2782 and 1391 patients per group to be 90% certain that the upper limit of the one-sided 95% confidence interval will exclude a difference in favor of the standard group of > 1.89%. The calculation of the final overall population with a 5% loss is 2922, 1461 patients per group.

In the Cath-lab at the Instituto Nacional de Cardiología Ignacio Chávez, 4608 procedures are performed per year, of which 3600 are in adults with ischemic and structural heart disease. Of this total group, 2880 are PCI. Approximately 90 procedures per month or 1080 per year correspond to patients with SICA; of these patients, approximately 65% (702) correspond to STEMI; thus, at least our institute would contribute 2106 patients for this multicenter study, which corresponds to 75% of the total population required; the rest of the centers should only contribute 766 patients. It is feasible to carry out the study over a period of 36 months.

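### The 2782 patients correspond to 80% power with no true difference, not to 90% certainty under a true 1.89-point benefit of distal access

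*Combined protocol and SAP*

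**What the plan says.** Everything on this point is in the Sample size section under METHODOLOGY. It opens with "The significance level (Alpha) will be 5%, power (1-beta) 80" per cent. The composite event rate "in the CR group was set at 4.19% based on the RIVAL study and with a non-inferiority cutoff of 1.89" per cent, so the control rate is 4.19% and the margin is 1.89 percentage points.

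The next sentence gives the alternative: "In the presence of a true difference in favor of the experimental group of 1.89" per cent. The section then says that under this alternative "the total population required is 2782 and 1391 patients per group to be 90% certain that the upper limit of the one-sided 95% confidence" bound rules out an advantage of the standard group larger than the margin. A 5% loss allowance then brings the total to 2922, or 1461 per group.

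The STATISTICAL ANALYSIS PLAN section does not restate power, significance level, margin or alternative, so nothing elsewhere reconciles the figures.

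**The concern.** The probability that the upper confidence limit falls below the margin is the power of a non-inferiority trial. The section therefore gives two powers, 80% and 90%, for one sample size, one margin and one confidence level. It also uses 1.89 points twice, as the margin and as the assumed true advantage of distal access. An assumed advantage of that size doubles the distance between the true difference and the margin and should shrink the trial sharply, yet 2782 is a large number.

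This is the only statement of the trial's operating characteristics. A reader may conclude that the trial has 90% power, or that it was sized on an expected advantage in net clinical events. The STATEMENT OF THE PROBLEM section says there is no evidence that distal access is superior or non-inferior on that outcome in STEMI. A result that fails to show non-inferiority will be read differently if its prior probability under true equality was 20% rather than 10%.

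**Working it through.** **Inputs, all from the Sample size section.** Control rate pC = 0.0419. Margin M = 0.0189. One-sided 95% confidence interval, so one-sided alpha = 0.05 and z = 1.645. Allocation 1:1. Power 80% (z = 0.842) or 90% (z = 1.282). True distal-access rate pE = 0.0419 for no difference, or 0.0419 − 0.0189 = 0.0230 for the stated benefit.

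**Formula.** The outcome is an adverse event, so a true benefit adds to the margin:

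n per group = (z_alpha + z_beta)² × [pC(1 − pC) + pE(1 − pE)] / (M + pC − pE)²

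**Step 1: reproduce the stated figure.** With no true difference the variance term is 2 × 0.0419 × 0.9581 = 0.08029, and the denominator is 0.0189² = 0.00035721. At 80% power, n = 1389.6, i.e. 1390 per group. With the z values rounded to 1.645 and 0.842, (2.487)² × 0.08029 / 0.00035721 = 1390.2, which rounds up to 1391. The stated number is reproduced.

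**Step 2: try the stated combinations.** With the stated benefit the variance term is 0.04014 + 0.0230 × 0.9770 = 0.06262, and the denominator is (0.0378)² = 0.00142884.

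| Power | True difference | n per group | Total | Gives 2782? |
|---|---|---|---|---|
| 80% | none | 1390 | 2780 | yes |
| 90% | none | 1925 | 3850 | no |
| 80% | 1.89 points in favour of distal | 271 | 542 | no |
| 90% | 1.89 points in favour of distal | 376 | 752 | no |

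**Step 3: power at 1391 per group.** Power = Φ[(M + pC − pE)/SE − 1.645].

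- No difference: SE = √(0.08029/1391) = 0.00760; 0.0189/0.00760 = 2.488; 2.488 − 1.645 = 0.843; power 80.0%.
- Stated benefit: SE = √(0.06262/1391) = 0.00671; 0.0378/0.00671 = 5.634; 5.634 − 1.645 = 3.989; power above 99.99%.
- For exactly 90% at this sample size, the true benefit would have to be about 0.30 points, a figure that appears nowhere in the plan.

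**Step 4: other methods.** A restricted maximum-likelihood (Farrington-Manning) variance gives about 1429 per group at 80% and 1971 at 90% with no difference. A continuity correction gives 1494 and 2030. At one-sided 2.5% the basic formula gives 1765 and 2362. A superiority comparison of 4.19% with 2.30% gives 1376 to 1379 per group at 80% and 1842 to 1846 at 90% (two-sided 5%); at one-sided 5% and 90% it gives 1502 to 1504. No variant tried at 90% power gives 1391.

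**Step 5: loss allowance.** 2782 × 1.05 = 2921.1, which becomes 2922 for equal arms. To retain 2782 after a 5% loss requires 2782/0.95 = 2929, or 2930 for equal arms.

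**The case against.** The strongest reply is that the section formally declares 80% power in its first sentence and the sample size delivers it. On this view the 90% is a slip and the design itself is sound. It can be added that, under the benefit the sentence literally assumes, power exceeds 99.99%, so the 90% is not overstated; the shortfall appears only when zero difference is put in place of the stated alternative. Both points are correct. They limit the charge to two stated powers, of which one is met, together with an alternative that did not generate the number. They do not make the sentence right, because its power and its alternative together give 752 patients, not 2782.

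A second reply is that a two-sided 5% superiority comparison of 4.19% with 2.30% at 80% power comes within about 1% of 1391 and does use the 1.89-point difference. The origin of 2782 is therefore inferred, not documented. But that calculation has no margin and no one-sided interval, it does not address the non-inferiority question in the RESEARCH QUESTION and HYPOTHESIS sections, it fits less closely, and it too needs 80%.

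A third reply is that arithmetic cannot show which power the sponsor intended. That stands, and the fix depends on the sponsor's confirmation. The loss allowance is 7 to 8 patients short, about 0.3%, and carries no weight in the conclusion.

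**Conclusion.** The concern holds. For the non-inferiority design described, 2782 is the sample size for 80% power with 4.19% in both arms and one-sided 5%. The stated 90% and the stated 1.89-point benefit do not produce it, separately or together. If the accesses are equivalent, the probability of failing to show non-inferiority is 20%, twice the 10% implied by the later sentence. Reaching 90% under equality would take 3850 evaluable patients, 1068 more than planned.

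These figures rest on the normal approximation with unpooled variance, the 4.19% control rate and the one-sided 95% interval named in the section. If non-inferiority were instead judged on a two-sided 95% interval (one-sided 2.5%), power at 1391 per group with no difference would be 70.1%; the plan does not specify that, and the conclusion does not depend on it.

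**What to change.** State one power and one alternative, and make the number follow from them. If the sponsor confirms 80% as intended, the sentence can be replaced by:

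> Assuming a 4.19% event rate in both groups (no true difference), 1391 evaluable patients per group (2782 in total) give 80% power that the upper limit of the one-sided 95% confidence interval for the difference (distal minus conventional) excludes an excess of 1.89 percentage points or more with distal access.

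The 90% certainty and the assumed 1.89-point true benefit should then be deleted. The enrolment target of 2922 can stay, or be restated as 2930 if the allowance is to cover a full 5% loss.

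On this route the cost is wording only: no patients are added, and the stated power becomes less favourable. If the sponsor in fact intended 90% with no true difference, rewording is not enough, and the sample size must be recalculated to about 3850 evaluable patients.

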### Specification of the variables

Independent: distal and proximal radial access.

Dependent: age, gender, body weight, body mass index, diabetes mellitus, systemic arterial hypertension, smoking, chronic obstructive pulmonary disease, dyslipidemia, overall death, cardiovascular death, myocardial infarction, vascular complications, vascular access bleeding, stent thrombosis, new revascularization of the treated vessel, cerebral vascular event, radial artery thrombosis, culprit vessel, stent type, left ventricular ejection fraction, troponin levels, ECG ST segment changes, ECG T wave changes.

### Data collection technique

The EXCEL database will be used to record all the variables selected, and the SPSS 2020 package will be used for the statistical analysis of the study and comparison of the variables.

## STATISTICAL ANALYSIS PLAN

The SPSS 2020 package will be used for the statistical analysis as described above. No interim analysis has been pre-specified. The analysis will be by treatment intention according to assignment. Categorical variables will be expressed as percentages, and continuous variables as means  $\pm$  standard deviation. To compare categorical variables, the chi-square test or Fisher's exact test will be used, and to compare continuous variables, the Student's t-test or Mann-Whitney U test will be used. Survival

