**Unique Protocol ID: 23-1367**

**BACKGROUND**

The radial artery (RA) is considered to be the vascular access of choice to perform percutaneous coronary intervention (PCI). (1, 2) The main advantage of conventional radial access (CRA) compared to femoral artery access is the reduction in major vascular complications and major bleeding. (3) This benefit reduces the rate of major adverse events and cardiovascular mortality. Outstanding randomized studies have confirmed the superiority of RA associated with a lower rate of vascular complications and mortality. (4, 5) The MATRIX study (Minimizing adverse haemorrhagic events by transradial access site and systemic implementation of angiox) demonstrated lower global mortality at 30 days with RA in patients with Acute Coronary Syndrome (ACS) (1.65 vs. 2.2%,  $p=0.045$ ). (6) This reduction was also demonstrated in the rate of compound events of death, myocardial infarction (MI), cerebrovascular event, and BARC type 3 or 5 (9.8% vs. 11.7%,  $p=0.0092$ ). (6, 7) In the RIVAL study (Radial versus femoral Access for percutaneous coronary intervention) the effectiveness of RA was similar to femoral access, with a lower rate of local vascular complications. (8) A subsequent analysis of the same study documented a greater benefit of RA in reducing net clinical adverse events and mortality in patients with AMI (Acute Myocardial Infarction) and elevation of the ST segment (STEMI). (9) The combination of events of death, MI, cerebrovascular event, or major bleeding was 4.19% with RCA and 8.18% with femoral access ( $p<0.001$ ) in patients with STEMI.

Distal radial access (DRA) has emerged as an alternative to CRA in PCI. (10) Compared to CRA access, RDA is associated with a lower rate of radial artery occlusion (RAO) and hematoma (10);

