**Instituto Nacional de Cardiología Ignacio Chávez**  
*Renacimiento de la Excelencia*

however, it requires more time for radial artery cannulation, more puncture attempts, and a higher rate of conversion to femoral. (10, 11)

There is no evidence that RDA is superior to CRA in patients with STEMI undergoing interventional treatment in relation to net adverse clinical events.

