### **STATEMENT OF THE PROBLEM**

Randomized studies have shown that DRA is associated with lower local complication rates than CRA access, primarily reducing the rate of RAO. A recent meta-analysis documented a 68% reduction in the relative risk ratio (RRR) of RAO at 24 hours with RDA and 64% RRR of RAO at longer follow-up. (10) In addition, a reduction in local complications, mainly hematomas, has been reported. However, the need to change vascular access is greater with the RDA. At present, there is no evidence to support that the RDA is superior or non-inferior to the CRA in relation to the rate of net adverse clinical events in patients with STEMI receiving interventional treatment. This aspect should be studied in order to determine the place that the RDA should occupy in the context of interventional treatment for STEMI.

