### **RESEARCH QUESTION**

Is the 30-day net adverse clinical event rate at 30 days in patients with STEMI undergoing PCI non-inferior when comparing DRA with CRA?

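### The SAP does not apply the non-inferiority criterion from the sample-size section, and the elimination rule contradicts analysis by assignment

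*Combined protocol and SAP*

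**What the plan says.** **The question and criterion.** The Research Question asks whether the 30-day event rate in STEMI patients is, in its words, "undergoing PCI non-inferior when comparing DRA with CRA". The Sample size section sets a CRA rate of 4.19%, a cutoff of 1.89% and 1391 patients per group. It frames success as the "upper limit of the one-sided 95% confidence interval will exclude a difference in favor of the standard group" larger than that cutoff.

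**The analysis.** The Statistical Analysis Plan states: "The analysis will be by treatment intention according to assignment". For comparisons it says: "To compare categorical variables, the chi-square test" or Fisher's exact test, with t or Mann-Whitney tests for continuous variables. It adds Kaplan-Meier curves, and conditional logistic regression relating baseline characteristics to events. It gives no cutoff, no confidence limit for the DRA minus CRA difference and no decision rule.

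**Who is analysed.** The Elimination criteria remove patients who withdraw or do not complete 30-day follow-up. The Sample size section allows for such losses: "The calculation of the final overall population with a 5% loss is 2922". No method for missing outcomes is given.

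**Change of access.** The Statement of the Problem says: "However, the need to change vascular access is greater with the RDA". The Background lists, for DRA, "more puncture attempts, and a higher rate of conversion to femoral". The Specification of the variables lists distal and proximal radial access, but no femoral or crossover item.

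**The concern.** A test of no difference and a non-inferiority test answer different questions. A non-significant chi-square may mean only that the data are imprecise, and it can occur when the upper limit lies well above 1.89 points. The Hypothesis section adds to the risk, because its null is worded as a question about a difference, which invites a reader to take failure to find one as success. What is at stake is a claim of non-inferiority that the trial's own criterion would reject.

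The elimination rule leaves the analysis set unclear. Analysis by assignment keeps every randomised patient in the assigned arm, whereas the elimination rule drops some of them for reasons that arise after randomisation. In an open-label trial those reasons need not be the same in both arms.

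If the access actually used is not recorded, readers also cannot see how often each strategy was carried out as assigned.

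**Working it through.** **Inputs.** From the Sample size section: CRA rate 4.19%, cutoff 1.89 points, one-sided 95% limit, 1391 per arm before loss and 1461 after. From the SAP: chi-square or Fisher's exact test.

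**1. Reproducing the plan's figure.** With equal true rates, one-sided 5% and 80% power:

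n = 2 × 0.0419 × 0.9581 × (1.645 + 0.842)² / 0.0189² ≈ 1390 per arm, against 1391 stated.

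The design therefore rests on the upper-limit criterion. (The same section also mentions 90% certainty and a true DRA benefit of 1.89 points. Neither reproduces 1391. That is a separate matter and does not change the criterion.)

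**2. Criterion against chi-square.** Expected CRA events are 0.0419 × 1391 = 58.3, taken as 58. The upper limit is

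UL = pE − pC + 1.645 × √[pE(1 − pE)/n + pC(1 − pC)/n], with n = 1391 and pC = 58/1391.

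| DRA events | Difference (points) | SE (points) | UL (points) | Criterion | Uncorrected chi-square p |
|---|---|---|---|---|---|
| 66 | 0.575 | 0.782 | 1.86 | met | 0.46 |
| 67 | 0.647 | 0.785 | 1.94 | fails | 0.41 |
| 80 | 1.582 | 0.823 | 2.94 | fails | 0.055 |
| 81 | 1.653 | 0.826 | 3.01 | fails | 0.045 |

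From 67 to 80 DRA events the chi-square test finds no significant difference while the criterion fails. Fisher's test extends this zone by one event (81 v 58, p = 0.055; 82 v 58, p = 0.046). A Farrington-Manning test switches at the same place as the upper limit (p = 0.0485 at 66, 0.0589 at 67).

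**3. How often this happens if DRA is truly worse by the cutoff.** Take true rates of 4.19% + 1.89% = 6.08% and 4.19%.

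- Pooled SE = √(2 × 0.05135 × 0.94865/1391) = 0.837 points; unpooled SE = 0.836 points.
- P(chi-square non-significant) ≈ Φ[(1.96 × 0.837 − 1.89)/0.836] = Φ(−0.30) ≈ 0.38.
- P(criterion met) is about 0.05 by construction.

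A simulation of 400,000 trials gives 0.379 and 0.051.

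**4. Size of the elimination problem.** The allowance is 2922 − 2782 = 140 patients, or 70 per arm. At 4.19% these carry 70 × 0.0419 ≈ 2.9 events per arm. Suppose completers are equal at 58 v 58 of 1391, and 3 of the 70 missing CRA patients had an event, giving 61/1461.

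- 12 events among 70 missing DRA patients: 70/1461 v 61/1461, UL 1.88, met.
- 13 events: 71/1461 v 61/1461, UL 1.95, fails.

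The result turns at 13/70 = 18.6% against 3/70 = 4.3%. If completers were 62 v 58, it turns at 9/70 = 12.9%, because 62 + 9 = 71. These are tipping points, not forecasts.

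**5. Crossover.** The documents give no conversion rate for either arm and no event rate in converters, so nothing can be calculated from them.

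**The case against.** **The criterion is in the document.** This stands: protocol and SAP are one document, and the Sample size section states the cutoff and the limit. The SAP assigns chi-square and Fisher's tests to categorical variables in general and does not call either the primary non-inferiority test. A reader might infer that the trial has no non-inferiority criterion, or that it plans to declare success on a non-significant chi-square. The text supports neither. The 67 to 80 zone shows a misreading that the plan leaves open. What remains is that no other analysis in the SAP compares the arms on the composite by a stated rule. The regression concerns baseline characteristics, and no comparison is attached to the Kaplan-Meier curves.

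**The missing-data scenario is extreme.** This also stands. Setting 140 lost patients against 58 events per arm would exaggerate the scale, since about 3 events per arm are expected among the missing. Kaplan-Meier could use data up to withdrawal. But the contradiction over who is analysed remains, whatever its numerical effect.

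**Crossover and per-protocol analysis.** A reader might infer that access changes bias the analysis by assignment or cost power, so that a per-protocol analysis is required. The documents do not support this. Conversion after a failed DRA attempt is part of the DRA strategy, so analysis by assignment validly compares strategies. Even the direction of any departure from the effect of the access used depends on assumptions. With a true excess of 1.89 points and 1391 per arm:

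- If converters took the CRA risk, the chance of meeting the criterion would be 6.3%, 7.8% and 9.7% at an assumed 5%, 10% and 15% conversion.
- If they went to femoral access at 8.18%, it would be about 3.8%, 2.9% and 2.2%.

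Femoral conversion is the only route the Background names. The 8.18% comes from the contrast "4.19% with RCA and 8.18% with femoral access", an access comparison in another trial whose composite includes major bleeding, so it is not a rate in patients with failed DRA.

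**Conclusion.** The point holds in two parts. First, the SAP does not carry the one-sided 95% upper limit and the 1.89-point cutoff into the primary analysis, and the only test it names for categorical outcomes cannot show non-inferiority. At 58 CRA events the two can disagree over 67 to 80 DRA events. This size assumes 1391 analysed per arm, a CRA rate near 4.19% and an uncorrected chi-square.

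Second, the elimination rule contradicts analysis by assignment. Its likely numerical effect is small: with equal completers and 70 missing per arm, the conclusion changes only with a strong imbalance, such as 13 events in DRA against 3 in CRA.

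A lesser gap is that no crossover item is listed although more access change is expected with DRA. No bias or loss of power from crossover is claimed.

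**What to change.** 1. State in the SAP that the primary analysis is the DRA minus CRA risk difference in the 30-day composite, in all randomised patients as assigned, with its one-sided 95% upper limit compared with 1.89 points. Add that a non-significant chi-square or Fisher test is not evidence of non-inferiority.
2. Reconcile the Elimination criteria with the SAP so that patients who withdraw or have incomplete follow-up stay in the by-assignment set with data up to withdrawal. State the method for missing 30-day outcomes, and add a sensitivity analysis that varies the event rate among missing patients by arm.
3. Record the access actually used, including femoral, and report crossover by arm. A per-protocol analysis is optional and supportive only, with no decision rule attached, because that set is not protected by randomisation and leaves out events in converters.

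The cost is SAP wording, one or two data fields and a little more analysis, with no change in sample size. The wording should be settled before outcome data are analysed. The access fields are needed as patients are treated, since that information may be hard to recover later.

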### **HYPOTHESIS**

H0: Is there a difference between the 30-day net adverse clinical event rates in patients with STEMI undergoing PCI when comparing DRA with CRA?

H1: The 30-day net adverse clinical event rate in patients with STEMI undergoing PCI is non-inferior when comparing DRA and CRA.

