**Instituto Nacional de Cardiología Ignacio Chávez**

*Renacimiento de la Excelencia*

curves will be constructed using the Kaplan-Meier method. Conditional logistic regression models will be obtained to obtain OR and CI to establish the association of baseline patient characteristics and net adverse clinical events. The pre-specified subgroup for analysis is STEMI.

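### The non-inferiority criterion in the sample-size text is not carried into the SAP, whose only test for a binary endpoint is a test of equality; H0 has no margin

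*Combined protocol and SAP*

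**What the plan says.** All places are in the combined protocol and SAP.

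- **Research Question.** The question is one of non-inferiority: "Is the 30-day net adverse clinical event rate at 30 days in patients with STEMI undergoing PCI non-inferior when comparing DRA with CRA".
- **Hypothesis.** The null is worded as a question: "H0: Is there a difference between the 30-day net adverse clinical event rates in patients with STEMI undergoing PCI when comparing DRA with CRA". The alternative is a non-inferiority statement: "H1: The 30-day net adverse clinical event rate in patients with STEMI undergoing PCI is non-inferior when comparing DRA and CRA". Neither contains a margin.
- **Methodology, Sample size.** The CRA event rate is 4.19% and the non-inferiority cutoff is 1.89%. The sample is meant to give assurance that "the upper limit of the one-sided 95% confidence interval will exclude a difference in favor of the standard group of > 1.89" percent.
- **Statistical Analysis Plan.** Analysis is by assigned group. For categorical variables it says "To compare categorical variables, the chi-square test" or Fisher's exact test. Continuous variables get the t-test or Mann-Whitney test. Kaplan-Meier curves are planned with no test attached. Conditional logistic regression is planned "to establish the association of baseline patient characteristics and net adverse clinical events"; the odds ratios from it are the only quantities in the section given a confidence interval.

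**The concern.** Non-inferiority is shown by placing an upper bound on how much worse the new route could be and comparing that bound with a margin. A chi-square or Fisher test asks whether the two rates are equal. The two can disagree: a trial can find no significant difference while its data remain compatible with an excess above 1.89 points.

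The SAP assigns no analysis to the primary composite. Of the methods it lists, only the equality tests compare a binary outcome between arms. The curves carry no inference, and the regression concerns baseline characteristics, not access route. H0 as written is not the complement of H1, so rejecting it would not establish H1.

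The trial's main conclusion is at stake. It would rest on a criterion that appears only in the text justifying the sample size, with no named interval method. Because the trial is open-label, leaving the method and the rule unstated also leaves room to choose them once results are known.

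**Working it through.** **Inputs.** From Sample size: CRA rate 4.19%; margin 1.89 points; alpha 5%, used one-sided as the confidence-limit sentence implies; power 80%; 1391 per arm, or 1461 after the loss allowance. From the SAP: chi-square or Fisher. Assumptions: equality tests are two-sided at 5%, and the upper limit is a Wald limit. Probabilities come from exact enumeration of two binomial distributions.

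**1. The plan's own figure.** With equal true rates,

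n = 2p(1 − p)(z₀.₉₅ + z₀.₈₀)² / margin² = 2 × 0.0419 × 0.9581 × (1.645 + 0.842)² / 0.0189² ≈ 1390 per arm,

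against 1391 stated. At 1391 the exact probability that the upper limit falls below 1.89 points is 80.1%. The stated sample size therefore fits the criterion that the SAP leaves out, and adopting that criterion needs no more patients. The same section also states 90% certainty and a true 1.89-point advantage for DRA. Neither reproduces 1391 in a non-inferiority calculation, but that is a separate matter.

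**2. How the two rules relate if the routes are truly equal (4.19% in both arms, 1391 per arm, uncorrected chi-square).**

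| Equality test | Limit below 1.89 | Limit 1.89 or above |
|---|---|---|
| Significant, favours DRA | 2.5% | 0 |
| Not significant | 77.6% (80.1 − 2.5) | 17.4% |
| Significant, favours CRA | about 0 | 2.5% |

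The equality test is non-significant in 77.6 + 17.4 = 95.0% of trials, and within that row it does not say which column applies. The 17.4% becomes 18.0% with continuity correction and 17.9% with Fisher. At 1461 per arm the three figures are 15.8%, 16.3% and 16.3%.

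**3. A worked example: 1391 per arm, 58 CRA events (4.17%) and 70 DRA events (5.03%).**

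- Difference = 0.86 points.
- SE = √[(0.0417 × 0.9583 + 0.0503 × 0.9497) / 1391] = 0.794 points.
- Upper limit = 0.863 + 1.645 × 0.794 = 2.17 points, above 1.89, so non-inferiority is not shown.
- Chi-square p = 0.28; Fisher p = 0.32.

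**4. The range over which the rules part.** Each row takes the CRA count shown and gives the excess of DRA events for which the test is non-significant but the criterion fails.

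| Per arm | CRA events | Excess, uncorrected chi-square (upper limits) | Excess, Fisher (upper limits) |
|---|---|---|---|
| 1391 | 58 | 9 to 22 (1.94 to 2.93 points) | 9 to 23 (1.94 to 3.01 points) |
| 1461 | 61 | 10 to 23 (1.95 to 2.90 points) | 10 to 24 (1.95 to 2.97 points) |

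**5. A conditional figure.** Suppose non-significance were read as non-inferiority, which the SAP does not state. With DRA truly at the margin, 4.19 + 1.89 = 6.08%, the equality test is non-significant with probability 37.9% (uncorrected) or 41.4% (corrected or Fisher) at 1391 per arm, and 36.0% or 39.1% at 1461. The upper-limit criterion would wrongly declare non-inferiority in 5.2% and 5.1%.

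**The case against.** The strongest reply is that this is a single combined document. The sample-size section already fixes the margin, the interval, its level and its direction, and H1 names non-inferiority, so the rule is pre-specified and only a cross-reference is missing. On this reading the chi-square sentence is a general statement about categorical variables that never mentions the primary composite, so the fault is omission and not a wrong test.

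Part of this stands. The criterion does exist in the document, and applying chi-square to the primary composite is an inference from its being the only listed test that fits. But the sample-size text says what the number of patients should achieve. It does not designate a primary analysis or an interval method, and the SAP does not refer back to it for the analysis. If the chi-square sentence is only descriptive, the primary endpoint has no planned analysis at all.

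Three points about the numbers are also fair:

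- The 17.4% is not an error rate of the plan. At 1391 per arm the criterion fails in 100 − 80.1 = 19.9% of trials with equal rates by design, and the 17.4% lies within that. It measures how often the two rules part.
- The 36.0% to 41.4% figure depends on a reading that the SAP does not state and carries no weight in the conclusion.
- The match to 1391 is good evidence, not proof, of how the trial was sized: a two-sided superiority calculation of 4.19% against 2.30% at 80% power gives 1379. The concern does not need this inference.

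The wording of H0 adds little operational harm of its own, but it points the same way as the SAP.

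**Conclusion.** The concern holds, and the plan is wrong as written. The stated question is non-inferiority with a 1.89-point margin; the only stated analysis that fits the binary primary endpoint tests equality and cannot answer that question when it is non-significant. With a 4.19% rate in both arms, non-significance is expected in about 95% of trials. Across the two sample sizes and the three versions of the equality test, 15.8% to 18.0% of all trials would be non-significant and yet fail the sponsor's own criterion. These figures assume a Wald limit and two-sided 5% equality tests. The textual finding depends on none of them. Because it governs the primary conclusion, it must be corrected before outcome data are analysed.

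**What to change.** In **Hypothesis**, replace both statements with:

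> H0: p(DRA) − p(CRA) ≥ 1.89 percentage points. H1: p(DRA) − p(CRA) < 1.89 percentage points.

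In the **Statistical Analysis Plan**, add:

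> The primary analysis is the 30-day risk difference (DRA minus CRA) in the primary composite, with the upper limit of its one-sided 95% confidence interval by [named method]. Non-inferiority is concluded only if that limit is below 1.89 percentage points. Chi-square and Fisher tests are for baseline and secondary comparisons; a non-significant result is not evidence of non-inferiority.

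The interval method should be named in advance, but the choice matters little at this size. With DRA truly at the margin, the false-positive rate at 1391 per arm is 5.2% for the Wald limit and 5.0% for the Farrington-Manning score method.

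The cost is wording in two sections. The margin, significance level, number of patients and data collected stay as they are.
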